7.1.4 Month 1 Visit (± 7 days)

The following procedures and assessments will be performed at the Month 1 visit:

- Review of subject diary
- Weight measurement and assignment of IMP via IRT
- MRI assessment (see Section 7.3.1)
- Administration of trial medication
- Assessment of AEs, concomitant medications and concomitant procedures

Once all procedures and assessments for this visit are completed, an appointment for the next visit will be made and the subject will be discharged.

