8.2 Definition of Analysis Sets and Subgroups

Enrolled Set (ES)

All subjects enrolled in the study, i.e., all subjects with a signed informed consent.

Intent-to-treat Set (ITT)

All subjects classified as eligible (i.e., medication assigned by iRT at the Baseline Visit).

Full Analysis Set (FAS)

All subjects in the ITT treated with at least one dose of study medication.

Treatment Completer Set – Year 1 (TCS-1)

All subjects from the FAS who completed the full Treatment Course of the first year (Treatment Course 1). Subjects will be classified as Treatment Completer for the first year if they have a compliance greater than or equal to 100% for Treatment Course 1.

Treatment Completer Set – Year 2 (TCS-2)

All subjects from the FAS who completed the full Treatment Course of the first and the second year. Subjects will be classified as Treatment Completer for the second year if they have a compliance greater than or equal to 100% for Treatment Course 1 and Treatment Course 2 and received the treatment without delay (see Section 9 for definition).

Safety Analysis Set (SAF)

All subjects treated with at least one dose of study medication.

Unless otherwise specified, all efficacy analyses will be performed on the FAS.

Some tertiary analyses will be repeated on the Treatment Completer Sets and the primary analysis, on the ITT (if different from FAS), to evaluate the robustness of the primary results to deviations of the planned treatment regimen. Further details are given in the respective sections. All safety analyses will be performed on the SAF.

Additional Subgroup or Subset Analysis Sets

Subgroup analyses will be performed on subgroups as defined below.

- High-relapse activity (HRA)
 - HRA: at least 2 relapses in the previous year (i.e. the number of historical relapses within 12 months prior to Baseline ≥ 2) regardless of prior use of DMDs
 - Non-HRA: otherwise

Unless otherwise indicated, all descriptive statistical analyses will be presented separately for the HRA subgroups.

- Previous treatment with Disease Modifying Drugs (DMDs):
 - DMD pre-treated: Subjects will be categorized as DMD pre-treated if they have taken DMDs any time before start of study medication. Details of the definition of DMDs are specified in Appendix 1 (Section 18.1).
 - Pre-treatment naïve: all subjects not classified as DMD pre-treated.

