All relevant previous medications which are classified as DMDs will be presented by PT. DMDs which are taken within 6 months prior to start of study medication (i.e. DMD end date \geq start of study medication - 182.625) will be presented by PT. The length of the washout Period (start of study medication - DMD end date + 1) of the last DMD within 6 months prior to start of study medication will be summarized. The last DMD will be defined as the DMD with the latest stop date. If the DMD end date is partially missing, the day will be imputed by the 15th of the month but the date will be truncated to IC date -1 if the imputation results in a later date. If the month is missing as well or the date is completely missing the end date will not be replaced and it assumed that the DMD stopped earlier than 6 months prior to start of study medication.

Concomitant procedures which were undertaken any time on study will be listed by subject for the SAF.

13 Treatment Compliance and Exposure

Two years of treatment are planned in this study. Subjects will take tablets in Week 1 (Treatment week 1) and Week 5 (Treatment week 2) of each year. All dosing calculations and summaries will be based on “Treatment Administration” and “Treatment Termination” eCRFs pages.

The following summary tables will be provided for the SAF:

- Duration of therapy,
- Compliance and Drug Accountability

The duration will be presented for Treatment Course 1 Treatment Period, Treatment Course 2 Treatment Period and the Treatment Period in days.

- Duration (days)= (date of last tablet in Period – date of first tablet in Period + 1)

Counts of tablets and compliance will be calculated first for each treatment week:

- Compliance (%) = $100 * \text{number of tablets taken during the treatment week} / \text{number of planned tablets for the treatment week}$

If a subject discontinued the treatment before the start of the respective treatment week, compliance will not be derived for this week. If the subject did not take any tablet during the respective treatment week, but had not discontinued the treatment before, compliance will be 0. If the subject was treated during the respective treatment week, but the number of tablets is unknown, compliance will be missing.

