Compliance for each year (course) and total will be calculated for all subjects that started the respective treatment period (i.e. taken at least one tablet) as an average of available records obtained for the corresponding treatment weeks. That means, treatment weeks after the subject’s treatment discontinuation are not included in the derivation, records of 0 compliance for the corresponding treatment weeks are included in the derivation as such, and missing records result in missing compliance for the respective treatment period.

In addition, compliance will be categorized as follows:

- < 60%
- [60%-80%[
- [80%-90%[
- [90%-110%]
- >110%

The number of planned tablets is based on the weight at the beginning of each treatment course (Table 2).

Table 2: Dose of Mavenclad® per treatment week by subject weight in each treatment year

Weight range	Dose in mg (number tablets) per treatment week	
	Treatment week 1	Treatment week 5
40 to <50	40 mg (4 tablets)	40 mg (4 tablets)
50 to <60	50 mg (5 tablets)	50 mg (5 tablets)
60 to <70	60 mg (6 tablets)	60 mg (6 tablets)
70 to <80	70 mg (7 tablets)	70 mg (7 tablets)
80 to <90	80 mg (8 tablets)	70 mg (7 tablets)
90 to <100	90 mg (9 tablets)	80 mg (8 tablets)
100 to <110	100 mg (10 tablets)	90 mg (9 tablets)
110 and above	100 mg (10 tablets)	100 mg (10 tablets)

The number of subjects with the same planned dosing schema in both Treatments Courses and a different planned dosing schema (i.e. subjects exchanged weight range as defined in the table above) in Treatment Course 2 will be presented for all subjects, who have started Treatment Course 2 (i.e. taken at least one tablet in Treatment Course 2).

The time difference between the start of the Treatment Course 1 Treatment Period and the start of the Treatment Course 2 Treatment Period will be calculated as follows:

- Relative Start of Treatment Course 2 (days) = Start of Treatment Course 2 - Start of Treatment Course 1 + 1.

The Relative Start of Treatment Course 2 will be presented together with the number of subjects in the following groups for the SAF:

- Treatment Course 2 not started,
 - and discontinued before the Month 12 Visit,
 - and discontinued at or after Month 12 Visit
 - Lymphocyte count < 800 cells/mm³ at Month 12 Visit,
 - Reason potentially related to COVID-19
- Treatment Course 2 started,
 - and not delayed (see Section 9 for definition),
 - and delayed,

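### The Treatment Completer rule scores a subject who is recorded as stopping after treatment week 1 at 100% compliance, so a half-treated subject enters TCS-1

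*SAP*

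**What the plan says.** SAP Section 8.2 introduces TCS-1 as FAS subjects who completed the whole first-year course, and TCS-2 as those who completed both years' courses. It then gives the working rule. Subjects are "classified as Treatment Completer for the first year if they have a compliance greater than or equal to 100% for Treatment Course 1". For TCS-2 the requirement is "compliance greater than or equal to 100% for Treatment Course 1 and Treatment Course 2 and received the treatment without delay". Neither rule separately requires that both treatment weeks were taken.

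SAP Section 13 gives each course two treatment weeks (Week 1 and Week 5) and defines compliance in two stages:

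- **Weekly:** tablets taken divided by tablets planned, times 100. "If a subject discontinued the treatment before the start of the respective treatment week, compliance will not be derived for this week". A week in which a subject who had not discontinued took no tablet counts as 0.
- **Course:** calculated "as an average of available records obtained for the corresponding treatment weeks". The section then spells out that weeks after treatment discontinuation stay out of the calculation and that zeros stay in.

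Protocol Section 8.4 plans to repeat the primary analysis on the Treatment Completer Sets as a robustness analysis. SAP Section 8.2 says instead that some tertiary analyses will be repeated on these sets, to check robustness to departures from the planned regimen. In the SAP's analysis tables, TCS-1 and TCS-2 appear only in Section 14.3.1, for the yearly change in annualized CUA lesion count.

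**The concern.** The description in Section 8.2 and the rule that implements it can disagree. Compliance in Section 13 measures adherence while on treatment: it asks whether the subject took what was due before stopping. Course completion is a different quantity. Using the first as the only test for the second lets in a subject who took everything due in week 1 and then stopped.

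Membership also depends on how the stop was recorded. Two subjects with the same tablets taken fall on opposite sides of the threshold according to whether a discontinuation was entered before treatment week 2.

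Such subjects can supply data. Protocol Sections 5.2 and 5.5.1 keep subjects who stop the drug in the scheduled visits, MRI included. At stake is the meaning of the completer-set repeats: a set meant to hold fully treated subjects may contain half-treated ones.

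**Working it through.** **Inputs.** Planned tablets by weight band are in SAP Section 13, Table 2. The weekly and course compliance rules are in SAP Section 13, and the threshold of at least 100% is in SAP Section 8.2.

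**Formulas**

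- Weekly compliance = 100 × tablets taken / tablets planned.
- Course compliance = mean of the weekly values that exist. A week starting after discontinuation has no value; a week skipped without discontinuation has the value 0.

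**Reference case.** All tablets taken in both weeks: (100 + 100)/2 = 100%. The subject is a completer, as intended.

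**Case A: all of week 1 taken, discontinuation recorded before treatment week 2.** Only the week-1 value exists, so course compliance = 100/1 = 100% in every band. The share of the planned course actually taken is:

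| Weight band (kg) | Planned, week 1 + week 2 | Taken | Share of course | SAP compliance |
|---|---|---|---|---|
| 40 to <50 | 4 + 4 | 4 | 4/8 = 50.0% | 100% |
| 50 to <60 | 5 + 5 | 5 | 5/10 = 50.0% | 100% |
| 60 to <70 | 6 + 6 | 6 | 6/12 = 50.0% | 100% |
| 70 to <80 | 7 + 7 | 7 | 7/14 = 50.0% | 100% |
| 80 to <90 | 8 + 7 | 8 | 8/15 = 53.3% | 100% |
| 90 to <100 | 9 + 8 | 9 | 9/17 = 52.9% | 100% |
| 100 to <110 | 10 + 9 | 10 | 10/19 = 52.6% | 100% |
| 110 and above | 10 + 10 | 10 | 10/20 = 50.0% | 100% |

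**Case B: same tablets taken, week 2 skipped, no discontinuation recorded.** (100 + 0)/2 = 50% in every band. Excluded.

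**Case C: one tablet short in week 1, then discontinuation recorded.** From 3/4 = 75.0% in the lowest band to 9/10 = 90.0% in the two highest. Excluded. The gap therefore needs complete week-1 intake as well as a recorded stop.

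**TCS-2.** A subject in Case A during Course 1 who never starts Course 2 is not in TCS-2, because SAP Section 9 classes a Course 2 that never started as delayed and TCS-2 requires no delay. The route into TCS-2 is full Course 1, Course 2 started on time, all its week-1 tablets taken, and discontinuation recorded before its second week. Course 2 compliance is then 100% by the same calculation.

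**After the correction.** With week 2 counted as 0, Case A gives (100 + 0)/2 = 50.0% in every band. With total taken over total planned it gives 50.0% to 53.3%. The subject is excluded either way.

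**The case against.** The best defence is that dropping weeks after discontinuation is deliberate and clearly stated. It gives adherence on treatment, which is a legitimate quantity. Early stopping is reported elsewhere: discontinuations by reason in Section 10.1, duration of therapy and cumulative dose in Section 13. A reader might infer that the compliance table is wrong too. It is not; the table does what it says, and only its reuse as the completer test fails.

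It can also be said that Section 8.2 states its intent and that a programmer would follow it. The intent is indeed clear. But the compliance sentence is the only operational criterion, and in Case A it contradicts that intent.

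A reader might also infer the opposite misclassification. SAP Section 13 states that "The number of planned tablets is based on the weight at the beginning of each treatment course", while Protocol Section 7.1.4 lists "Weight measurement and assignment of IMP via IRT" at Month 1. A subject who changed weight band between the two weeks and took every assigned tablet might then seem to score below 100%. The documents do not support that conclusion. Protocol Section 7.1.3 and footnote 2 of the Schedule of Assessments both tie the dosing weight to the start of each course, which agrees with the SAP, and nothing says that the IRT changes the band at Month 1. What remains is a query to reconcile those passages.

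Finally, the reach is small. That stands: the primary analysis and the primary sensitivity analyses listed in SAP Section 14.1.2 do not use these sets.

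**Conclusion.** The rule as written misclassifies against its own description. A subject with full week-1 intake and a recorded stop before treatment week 2 meets the TCS-1 criterion with 50.0% to 53.3% of the course taken, while the same intake without a recorded stop gives 50% and exclusion.

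The effect is confined to the completer-set repeats: the yearly CUA change in the SAP, and the protocol's robustness repeat of the primary analysis if it is performed. It would be wrong to infer that the primary result is affected, or that TCS-2 is as open as TCS-1.

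The conclusion assumes that Section 8.2 is programmed from its compliance sentence. The documents give neither the number of such subjects nor the effect on any estimate. How much data they contribute to TCS-1 also depends on what date of discontinuation means in the SAP Section 9 definition of the Course 1 Treatment Period. If it means leaving the study, their MRI data up to Month 12 can count. If it means stopping the drug, their efficacy data after the stop are treated as missing.

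**What to change.** In SAP Section 8.2, for the definitions of TCS-1 and TCS-2 only, add that both treatment weeks of each relevant course must have been started, and that a week not taken counts as 0 in the course average whether or not discontinuation was recorded. Leave the on-treatment compliance derivation and table in Section 13 unchanged.

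An alternative is to require both weeks started and total tablets taken in the course divided by total planned for both weeks to be at least 100%. The two forms agree on every case above. They can differ when tablets move between weeks in a band with unequal weeks. For example, in the 80 to <90 kg band, 9 then 6 tablets averages (9/8 + 6/7)/2 = 99.1%, but the total is 15/15 = 100%. One form should be chosen and stated.

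The cost is a sentence or two and a small programming change. The completer sets may become slightly smaller.

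Separately, Protocol Sections 7.1.3 and 7.1.4, footnote 2 of the Schedule of Assessments and SAP Section 13 should be reconciled on which weight determines the planned tablets for treatment week 2.

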14.1.1 Primary Objective: Analysis of primary endpoints

The differences in counts of CUA lesions will be evaluated using a mixed-effects linear model, accounting for within-center/region correlation through a hierarchical model. The analysis will adjust for Baseline factors deemed to be prognostic for the primary endpoint, as judged by clinical experts:

- CUA lesion count during the Baseline Period,
- Age,
- EDSS at Baseline ($\leq 3 / > 3$).

The results of the mixed-effects linear model will be used to describe the effect size. A review of Baseline data has shown that the distribution of the primary endpoint data does not follow Normal distribution. Consequently, the hypotheses will be tested by a Wilcoxon signed-rank test which employs ranks of absolute differences from Baseline for each testing Period (i.e., p_1 , p_2 , and p_3) using average ranks for tied values.

The analysis will also adjust for the difference in length and number of MRIs of the Periods to be compared (see Section 9 “Data Handling of MRI data” for details of lesion count standardization).

The difference in the counts of CUA lesions during the three Periods compared to the Baseline Period will be tested in a sequential order. The three hypotheses are defined as follows:

$$H_{0i}: \Delta \text{CUA}(p_i) \geq 0 \quad \text{vs.} \quad \Delta \text{CUA}(p_i) < 0, \quad i = 1, 2, 3$$
$$\Leftrightarrow H_{0i}: \#\text{CUA}(p_i) \geq \#\text{CUA}(p_0) \text{ vs. } \#\text{CUA}(p_i) < \#\text{CUA}(p_0), \quad i = 1, 2, 3$$

with

$$\Delta \text{CUA}(p_i) = \#\text{CUA}(p_i) - \#\text{CUA}(p_0), \quad i = 1, 2, 3,$$

$$\#\text{CUA}(p_i): \text{standardized CUA lesion count during Period } p_i, \quad i = 0, 1, 2, 3,$$

p_0 : Baseline Period (Period from Screening to Baseline),

p_i : Period Month i to Month 6, $i = 1, 2, 3$.

The sequential testing procedure will start with Period p_3 , followed by Period p_2 and p_1 , i.e., the hypotheses will be tested in the following order:

1. H_{03}
2. H_{02}
3. H_{01}

The three hypotheses will be tested one-sided on a 2.5% significance level. The testing procedure will stop as soon as one of the hypotheses cannot be rejected following the pre-specified order. Due to this sequential order of tests an adjustment for a potential type-I-error inflation due to the multiple testing is not required.

An estimate for the difference in CUA lesions during the specified Periods compared to the Baseline Period will be reported, together with one-sided p-values. In addition, 95% CI and 2-sided p-values will be presented to allow for comparison with the 2-sided secondary and tertiary analyses.

The LS Means will be calculated with observed margin which reflects the distribution of age, EDSS categories at Baseline and respective Baseline Period CUA Lesion of the FAS. An unstructured covariance matrix will be assumed for the model. If the model doesn't converge a variance components covariance structure will be used instead or the results of sensitivity analysis with center effect as a fixed effect will be used instead.

Analysis (Analysis Set)	Derivation	Statistical Analysis Methods	Missing data handling
Primary endpoints: Differences in the counts of CUA MRI lesions during the first 6 months (i.e., during Periods months 1-6, 2-6, 3-6) compared to Baseline (i.e., the Period from Screening to Baseline) ^(a)			
Primary (FAS)	
 1. Period 3 (Month 3-6): $\Delta\text{CUA}(p_3)$ (Hypothesis 3) 2. Period 2 (Month 2-6): $\Delta\text{CUA}(p_2)$ (Hypothesis 2) 3. Period 1 (Month 1-6): $\Delta\text{CUA}(p_1)$ (Hypothesis 1) 	
P-values for the three Hypotheses from the Wilcoxon signed-rank test will be presented. The testing procedure will stop as soon as one of the hypotheses cannot be rejected following the pre-specified order (H3, H2, H1). Due to this sequential order of tests an adjustment for a potential type-I-error inflation due to the multiple testing is not required.
 
The Wilcoxon signed-rank test will be complemented by the estimated Least Square Means (LS Means) and corresponding Standard Errors (SE) including one-sided p-values as well as two-sided p-value and 95% CIs from the mixed-effects linear model with the following adjusting factors:
 
 • Baseline score, • Age (in years), • EDSS at Baseline (≤ 3, >3), • Within-pooled center correlation. 
In addition, the distribution of $\text{CUA}(p_i)$ and $\Delta\text{CUA}(p_i)$ will be displayed graphically using box plots.
	
Missing observations: Subjects with a missing CUA lesion count at either the Baseline Period or the respective post-Baseline Period will not be included in the analysis.

$\Delta\text{CUA}(p_i)$ = Difference in the standardized CUA lesion count between Period i and the Baseline Period (a) 6-month interim analysis
			

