8.5.2 Analysis of Primary Endpoints

The primary endpoint(s) for the trial are differences in counts of CUA MRI lesions during the first 6 months compared to baseline, i.e. the following differences will be evaluated:

- Period of month 3 to month 6 compared to the baseline period (i.e. the period of screening to baseline).
- Period of month 2 to month 6 compared to the baseline period,
- Period of month 1 to month 6 compared to the baseline period.

The differences in counts of CUA lesions will be evaluated using a mixed-effects linear model, accounting for within-center/region correlation through a hierarchical model.

The analysis will also adjust for baseline factors deemed to be prognostic for the primary endpoint, as judged by clinical experts:

- CUA lesion count during the baseline period,
- age,
- EDSS (≤ 3 / > 3).

The analysis will also adjust for the difference length and number of MRIs of the periods to be compared.

The difference in the counts of CUA lesions during the 3 periods compared to the baseline period will be tested in a sequential order. The 3 hypotheses are defined as follows:

$$H_{0i}: \Delta \text{CUA}(t_i) \geq 0 \quad \text{vs} \quad H_{1i}: \Delta \text{CUA}(t_i) < 0, \quad i=1,2,3$$

with

$$\Delta \text{CUA}(t_i) = \# \text{CUA}(p_i) - \# \text{CUA}(p_0), \quad i=1,2,3,$$

$$\# \text{CUA}(p_i): \text{count of CUA lesions during period } p_i, \quad i=0,1,2,3,$$

p_0 : baseline period (period screening to baseline),

p_i : period month i to month 6, $i=1,2,3$.

The sequential testing procedure will start with period p_3 , followed by period p_2 and p_1 , i.e., the hypotheses will be tested in the following order:

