 - and any Lymphocyte count < 800 cells/mm³ at or after Month 12 Visit and before start of Treatment Course 2.
- Before or at / after Start of COVID-19 pandemic

The cumulative dose is defined as the sum of the number of tablets taken 10 mg divided by the weight for treatment year:

Cumulative dose = number of tablets taken in Treatment Course 1 * 10mg / weight in kg at Baseline + number of tablets taken in Treatment Course 2 * 10mg / weight in kg at Month 12b Visit.

The cumulative dose will be calculated only if the weight and number of tablets are available. Otherwise it will be missing. If the Treatment Course 2 wasn't started (i.e. no tablet taken in Treatment Course 2), the cumulative dose will be calculated only for the Treatment Course 1.

A subject data listing of the treatment compliance will be provided for the SAF.

14 Efficacy Analyses

The following sections describe the planned analyses for each of efficacy endpoints.

For the detailed definition of covariates and stratification factors that are used in the statistical models see Section 9. Details about the derived MRI endpoints and general handling of MRI data is described in Section 9 (“Data Handling of MRI data”).

Descriptive summary statistics will be presented for the absolute values and the changes from Baseline as applicable by Visit [Protocol Scheduled Visits except for Baseline (defined in Section 9)], or Period, for all efficacy endpoints (and the components, where applicable) for the FAS and respective subgroups or subsets for which the variables are analyzed. Details about the presentation of continuous and categorical variables are given in Section 9.

Wherever possible, all estimated results from the statistical models will be calculated with the same observed margin which reflects the population of the whole corresponding analysis set, regardless of missing data.

14.1 Primary Endpoints: Differences in the counts of CUA MRI lesions during the first 6 months compared to Baseline

The primary endpoints for the trial are defined as the differences in counts of CUA MRI lesions during the first 6 months compared to Baseline, i.e., the following differences will be evaluated:

1. Period of Month 1 to Month 6 compared to the Baseline Period.
2. Period of Month 2 to Month 6 compared to the Baseline Period.
3. Period of Month 3 to Month 6 compared to the Baseline Period.

For the detailed definition of Periods, please see Section 9 “Data Handling of MRI data”.

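### The SAP 14.1.1 effect-size model treats the observed Baseline CUA margin as known in a single-arm change, so its 95% CIs are too narrow and its model p-values too small

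*SAP*

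**What the plan says.** The outcome in SAP 14.1.1 is defined under the analysis table as "Difference in the standardized CUA lesion count between Period i and the Baseline Period". The trial has a single arm (Protocol 5.2).

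The model adjusts that change for "CUA lesion count during the Baseline Period", age and EDSS category, with correlation within pooled center. Protocol 8.5.2 is the source of the covariates: "The analysis will also adjust for baseline factors deemed to be prognostic for the primary endpoint, as judged by clinical experts".

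On the evaluation point, SAP 14.1.1 says: "The LS Means will be calculated with observed margin which reflects the distribution of age, EDSS categories at Baseline". The sentence continues with the Baseline Period CUA count of the FAS. The introduction to SAP section 14 makes this a general rule: "all estimated results from the statistical models will be calculated with the same observed margin which reflects the population of the whole corresponding analysis set".

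The Primary (FAS) row of the table supplements the Wilcoxon test with LS means and SEs, "including one-sided p-values as well as two-sided p-value and 95% CIs from the mixed-effects linear model with the following adjusting factors". SAP 14.1.1 gives this model the role of describing effect size and gives the hypothesis tests to the Wilcoxon signed-rank test. Neither document carries the sampling variance of the Baseline margin into the model's SE.

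**The concern.** The Baseline count is both half of the outcome and a covariate. A sample that happens to have a high Baseline mean will show a fall without any drug effect. In a two-arm contrast that chance variation is shared and drops out. Here there is no second arm, so it remains part of the uncertainty about the mean change, and the model SE leaves it out.

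The Wilcoxon test gives a p-value but no effect size. The only 95% CI that SAP 14.1.1 plans for the primary difference, on the lesion-count scale, is the one from this model. A reader quoting how far lesion activity fell, and how precisely, would quote this interval. The shortfall is largest when the drug works, because the slope of change on Baseline then moves toward −1.

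**Working it through.** **No figure to reproduce.** The sample-size section is redacted, so the only stated benchmarks are nominal: one-sided 2.5% and 95% CI.

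**Inputs.** From the documents: the outcome, covariates, margin rule and single arm, as above, and about 265 planned subjects. Assumed, because the documents do not give them: the Baseline/post correlation ρ, the ratio k = SD post / SD Baseline, and for simulation 250 evaluable subjects.

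**Algebra.** Let D = Y1 − Y0. Regress D on Y0; the slope is b = ρk − 1. In a single-level model with the same subjects in the fit and the margin, the LS mean at the observed mean of Y0 equals mean(D).

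- Variance reported by the model: σe²/n = SD1²(1 − ρ²)/n
- Sampling variance of mean(D): σe²/n + b² Var(Y0)/n = (SD0² + SD1² − 2ρ·SD0·SD1)/n
- SE ratio (reported / correct): √[k²(1 − ρ²) / (1 + k² − 2ρk)]
- True coverage: 2Φ(1.96 × ratio) − 1. True one-sided error of the model p-value: 1 − Φ(1.96 × ratio)

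The ratio never exceeds 1, and equals 1 only when b = 0. With k = 1 it reduces to √[(1 + ρ)/2].

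| k | ρ | b | SE ratio | Coverage of 95% CI |
|---|---|---|---|---|
| 1 (no change) | 0.2 | −0.80 | 0.775 | 87.1% |
| 1 | 0.3 | −0.70 | 0.806 | 88.6% |
| 1 | 0.5 | −0.50 | 0.866 | 91.0% |
| 1 | 0.8 | −0.20 | 0.949 | 93.7% |
| 0.5 (post SD halved) | 0.3 | −0.85 | 0.489 | 66.3% |
| 0.5 | 0.5 | −0.75 | 0.500 | 67.3% |
| 0.5 | 0.8 | −0.60 | 0.447 | 61.9% |

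Worked row, k = 0.5 and ρ = 0.5: √[0.25 × 0.75 / (1 + 0.25 − 0.5)] = √(0.1875/0.75) = 0.50.

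For the k = 1 rows the one-sided error of the model p-value is 6.5%, 5.7%, 4.5% and 3.2%, against 2.5% nominal.

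**Simulation with the pooled-center random effect** (overdispersed counts, 22 pooled centers, covariates Y0, age and EDSS, 2,000 runs per setting; all assumed):

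| Setting | ρ | SE ratio | Coverage |
|---|---|---|---|
| No change | 0.83–0.86 | 0.99–1.01 | 94–95% |
| No change | 0.51–0.53 | 0.88–0.91 | 91–92% |
| No change | 0.29–0.31 | 0.77–0.80 | 86–88% |
| 60% fall | 0.27–0.78 | 0.32–0.43 | 47–60% |

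The same model without the Baseline covariate had SE ratios of 0.94–1.06 and coverage of 91.6–96.7%, with essentially the same point estimate. The fixed-center version, which SAP 14.1.1 also names as a fallback, did worse than the random-center model throughout (0.73–0.94 with no change, 0.30–0.41 with the fall).

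**Other effect sizes.** A separate simulation without center effects gave coverage of 56–67% for a 50% fall and 26–33% for an 80% fall. The unadjusted mean change, or the LS mean with the missing term added, covered 94–95%.

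**What a reader would see.** For a 60% fall, ρ about 0.5 and no center effect, the estimate is −0.90 with a reported SE of 0.068 against a true 0.157. The reported interval is −0.90 ± 1.96 × 0.068, or −1.03 to −0.77. The correct one is −0.90 ± 1.96 × 0.157, or −1.21 to −0.59.

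**The case against.** The other side has several good points.

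- **The trial's decision does not rest on this model.** A reader who starts from Protocol 8.5.2, where the mixed model is the planned analysis for the 2.5% tests, might infer that the primary type I error is inflated. The documents do not support that: SAP 14.1.1 moves the fixed-sequence tests to the Wilcoxon test on the paired differences. The model p-values decide nothing.
- **It is not the only effect size.** SAP sections 9 and 14 plan the mean and SD of the change by Period, from which a correct unadjusted interval can be computed. The negative binomial sensitivity model in SAP 14.1.2 treats Baseline as an outcome and gives a ratio with a CI free of this fault.
- **The size is assumed.** A reader might infer that the intervals are always far too narrow. With no change, equal SDs and ρ of 0.8 or more, the error is small. Some simulated one-sided errors under no change (6.4–11.1% at ρ about 0.3–0.5) exceed the closed form, so something beyond the omitted term, such as skewed counts, contributes.
- **Zero is not at issue under a large fall.** In the worked example both intervals exclude it.
- **The LS mean is not exactly the raw mean change.** Subjects with missing counts leave the fit while the margin reflects the whole FAS. Dropping the covariates would lose that standardization and depart from Protocol 8.5.2.
- **The primary analysis has been run.** SAP sections 6.2 and 7 say so, which means a silent rewrite of 14.1.1 would be a post-hoc change.

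All of this limits the scope and shapes the remedy. None of it restores the missing variance. The model interval is valid only conditional on this sample's Baseline counts, whereas the hypotheses concern the mean change itself.

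**Conclusion.** The point holds for precision only. For the population mean change, the SE in SAP 14.1.1 omits slope² × Var(Baseline)/n, so the 95% CIs are too narrow and the model's one- and two-sided p-values too small. The LS mean is not biased by this, and the confirmatory Wilcoxon sequence is untouched.

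The direction follows from the algebra; the size rests on assumed correlations, SDs and count distributions:

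- no change, equal SDs, correlation 0.8 or more: little error;
- no change, lower correlation: SE about 5–25% too small, coverage about 86–93%;
- a fall of 50% or more: SE about half the correct value or less, coverage about 67% or lower.

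The fault carries into every analysis that repeats the model: the subgroup, multiple-imputation and fixed-center versions in 14.1.2, and the CUA, T1 Gd+ and active T2 change models in 14.3.1, 14.3.3 and 14.3.7. A reader might extend the same alarm to 9HPT, T25FW and MTR, but nothing in the documents shows a material effect there. At an assumed correlation of 0.9 with equal SDs the ratio is √(1.9/2) = 0.975 and coverage 94.4%.

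**What to change.** Keep the pre-specified covariates and the LS mean. In SAP 14.1.1, take the SE, 95% CI and p-values from one of:

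1. a bootstrap over subjects that respects pooled center and recomputes the margins in each resample; or
2. the model's squared SE plus slope′ × Cov(covariates) × slope / n.

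Option 1 is safer if Baseline counts differ by center. In the simulation with center differences and a 60% fall, a plain one-sample t interval that ignored center covered only 88–90%, and option 2 with an ordinary covariance matrix ignores the same clustering. A third possibility is to report, beside the LS mean, the unadjusted mean change with its 95% CI from the random-center model.

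Because the Month 6 analysis has been run, report the corrected primary intervals in the study report as a labelled correction, and do not use the uncorrected model p-values. Apply the same rule to the 14.1.2 versions and to the change models in 14.3.1, 14.3.3 and 14.3.7. It may also be applied to 9HPT, T25FW and MTR, where little may change.

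Cost: wider intervals, a short SAP addition and a small program change. No new data are needed.
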